6.1 Number of subjects

Number of subjects planned to be screened (i.e. documented informed consent): 610

Number of subjects planned to be randomised: 426

Number of subjects expected to complete the trial: 340

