8.1.7 Withdrawn subjects

If a subject is withdrawn from the trial, the investigator must aim to undertake procedures similar to those for Visit 26 as soon as possible. The subject should also have the follow-up contact performed, if possible. The subjects should be requested to return all used, partly used and unused trial product.

The end-of-trial form must be completed, and final drug accountability must be performed even if the subject is not able to come to the trial site. A withdrawal session must be made in the IV/WRS. The case book must be signed.

Although a subject is not obliged to give his/her reason(s) for withdrawing from a trial, the investigator must make a reasonable effort to ascertain the reason(s), while fully respecting the subject's rights. Where the reasons are obtained, the primary reason for not completing the trial must be specified on the end-of-trial form in the eCRF.

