14.2 Titration Surveillance

An independent Novo Nordisk Titration Group will centrally perform insulin titration surveillance. This is also described in Section [5](#) of the Titration Guideline found in [Appendix A](#).

Surveillance will be performed on an on-going basis throughout the trial. The Novo Nordisk Titration Group reviews the information provided by the investigator in the eCRF after each visit/phone contact and follows-up on significant deviations from the titration guideline.

It is important that information regarding BIAsp 30, dose titration and hypoglycaemic episodes is entered within **24 hours** after the visit/phone contact. Data to be entered are described in Section [8.6.2](#).

15 Data management

Data management is the responsibility of Novo Nordisk.

Appropriate measures, including encryption of data files containing person identifiable data, will be used to ensure confidentiality of subject data, when they are transmitted over open networks.

Data from central laboratories will be transferred electronically. In cases where data is transferred via non-secure electronic networks, data will be encrypted during transfer. The laboratory will also provide all laboratory reports to the investigator for storage at the trial site.

The subject and any biological material obtained from the subject will be identified by subject number and trial ID. Appropriate measures such as encryption or leaving out certain identifiers will be enforced to protect the identity of subjects in all presentations and publications as required by local, regional and national requirements.

16 Computerised systems

Novo Nordisk will capture and process clinical data using computerised systems that are described in Novo Nordisk Standard Operating Procedures and IT architecture documentation. The use and control of these systems are documented.

Investigators working on the trial may use their own electronic systems to capture source data.

17 Statistical considerations

Novo Nordisk will be responsible for the statistical analysis and reporting. Analysis and reporting will be done with data from all sites pooled together.

The statistical analyses will be performed with a significance level of 5% (two-sided tests).

If necessary, a statistical analysis plan (SAP) may be written in addition to the protocol, including a more technical and detailed elaboration of the statistical analyses. The SAP will be finalised before database lock.

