17.1 Sample size calculation

The primary objective of this trial is to compare the efficacy of thrice daily BIAsp 30 versus twice daily BIAsp 30, both in combination with metformin, in subjects with type 2 diabetes inadequately controlled on basal insulin combined with OADs. The primary endpoint is change from baseline in HbA_{1c} after 24 weeks of treatment and the sample size is determined based on this endpoint.

Let D be the mean treatment difference for change in HbA_{1c} (BIAsp 30 TID minus BIAsp 30 BID). The null-hypothesis will be tested against the alternative hypothesis as given by

$H_0: D = 0\%$ against $H_A: D \neq 0\%$

Sample size is determined using a t-statistic under the assumption of a two-sided test and a significance level of 5%. Based on experience from previous trials^{19,20}, an estimated treatment difference of 0.3% and a standard deviation (SD) of 1.1% for HbA_{1c} will be used in the sample size calculation (see [Table 17-1](#)). The randomisation scheme will be 1:1. The sample size calculation is done using Statistical Analysis System (SAS) 9.3.

Table 17–1 Number of subjects required totally under different SD and different power requirement

Subjects in total	Estimated SD in HbA _{1c} (%)			
	1.0	1.1	1.2	1.3
Power				
80%	352	426	506	592
85%	402	486	578	678
90%	470	568	676	792
95%	580	702	834	978

Assuming a SD of 1.1%, a total of 426 subjects (213 subjects per group) in the FAS analysis set will give 80% power in detecting the treatment difference between BIAsp 30 TID and BIAsp 30 BID based on the primary endpoint.

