17.3 Primary endpoint

The primary objective of this trial is to compare the efficacy of thrice daily BIAsp 30 versus twice daily BIAsp 30, both in combination with metformin, in subjects with type 2 diabetes inadequately controlled on basal insulin combined with OADs.

The primary efficacy endpoint is the change from baseline in HbA_{1c} after 24 weeks of treatment. Change in HbA_{1c} from baseline to the 4, 8, 12, 16, 20 and 24 week’s measurements will be analysed using a Mixed Model for Repeated Measurements (MMRM), with treatment, combination of the two stratification factors (HbA_{1c} value and previous OAD treatment) and region (China/non-China)

as fixed factors and baseline HbA_{1c} as a covariate, all variables nested within visit as a factor. Region China includes China, Hong Kong and Taiwan and non-China includes all the other participating countries. An unstructured covariance matrix will be used to describe the variability for the repeated measurements for a subject. From the MMRM model the treatment difference at week 24 will be estimated and the corresponding 95% confidence interval and p-value will be calculated. All subjects in the FAS will be included in this analysis.

If p-value < 0.05, or equivalently, if the upper bound of the 95% confidence interval is below 0% or the lower bound of the 95% confidence interval is above 0%, the treatment difference will be regarded as statistically significant.

An important assumption for using MMRM is that the missing data are missing at random (MAR).

For this trial, missing data are mainly expected to occur due to withdrawal/discontinuation from the trial. Intermittent missing data (visits with missing data in between visits with data) is expected to be less common.

The main reasons for withdrawal/discontinuation are expected to be ineffective therapy and adverse events. Discontinuation due to ineffective therapy is expected to be MAR to some extent. For missing data due to adverse events, the MAR assumption may be questionable.

Sensitivity analyses will be performed for the primary efficacy endpoint. They will include:

- An analysis of covariance (ANCOVA) model with last observation carried forward (LOCF) imputation. Effects in the model are treatment, combination of the two stratification factors and region as factors, and baseline HbA_{1c} as a covariate.

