- A pattern mixture model approach mimicking an ITT scenario where withdrawn subjects are assumed to be switched to the control treatment (i.e., BIAsp 30 BID) after withdrawal. Multiple copies (100 copies) of the full dataset will be generated by imputing missing values based on estimated parameters for the control group. This will be done as follows:
 - In the first step intermittent missing values are imputed using a Markov Chain Monte Carlo method, in order to obtain a monotone missing data pattern. This imputation is done for each treatment group separately and 100 copies of the dataset will be generated.
 - In the second step, for each of the 100 copies of the dataset, an ANCOVA model with combination of the two stratification factors and region as factors and baseline HbA_{1c} and HbA_{1c} at 4 weeks as covariates is fitted to the change in HbA_{1c} from baseline to 8 weeks for the control group only. The estimated parameters, and their variances, from this model are used to impute missing values at 8 weeks for subjects

in both treatment groups, based on their combination of the two stratification factors and region and HbA_{1c} at baseline and 4 weeks.

- In the next steps, for each of the 100 copies of the dataset, missing HbA_{1c} values at 12, 16, 20 and 24 weeks are imputed sequentially in the same way as for 8 weeks. The imputations are based on an ANCOVA model with combination of the two stratification factors and region as factors and the HbA_{1c} values at baseline and previous post-baseline visits as covariates, fitted to the control group.
- After imputation, for each of the complete data sets, the change from baseline to Week 24 is analysed using an ANCOVA model with treatment, combination of the two stratification factors and region as factors, and the baseline HbA_{1c} value as a covariate.
- The estimates and standard deviations for the 100 data sets are pooled to one estimate and associated standard deviation using Rubin's formula:

$$m_{MI} = \frac{1}{100} \sum_{i=1}^{100} m_i, \quad SD_{MI} = \sqrt{\frac{1}{100} \sum_{i=1}^{100} SD_i^2 + \left(1 + \frac{1}{100}\right) \left(\frac{1}{100-1}\right) \sum_{i=1}^{100} (m_i - m_{MI})^2}$$

where m_i and SD_i are the estimated means and standard deviations for the 100 copies of the dataset, and m_{MI} , SD_{MI} are the pooled estimates.

- From m_{MI} and SD_{MI} , the 95% confidence interval for the treatment difference and the associated p-value are calculated.

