The dichotomous endpoints will be analysed by a logistic regression model. Effects in the model are treatment, combination of the two stratification factors and region as factors, and baseline HbA_{1c} as a covariate. The results will include the 95% confidence interval for the odds ratio (BIAsp 30 TID

over BIAsp 30 BID) and the p-value for test of no difference between the groups as part of the presentation.

For the dichotomous endpoint of HbA_{1c}<7% at week 24 (yes/no), missing HbA_{1c} values at week 24 will be imputed using the predicted value from an MMRM analysis. For the other two dichotomous endpoints, as a conservative approach, subjects withdrawn before 24 weeks will be handled as non-responders.

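### HbA1c <7.0% is tested after filling each missing week-24 value with one MMRM prediction treated as observed, so its interval is too narrow and its rate is not comparable with the composites

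*Combined protocol and SAP*

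**What the plan says.** Section 17.4.1.1 defines three yes/no endpoints at 24 weeks: HbA1c <7.0%, the same without severe hypoglycaemia, and the same without severe or BG-confirmed hypoglycaemia. All three go into a logistic regression with treatment, combined strata, region and baseline HbA1c, reported as an odds ratio with 95% interval and p-value.

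The missing-data rules differ. For HbA1c <7.0%, "missing HbA_{1c} values at week 24 will be imputed using the predicted value from an MMRM analysis". For the two composites, described as handled conservatively, "subjects withdrawn before 24 weeks will be handled as non-responders". No multiple imputation, variance correction or sensitivity analysis is given for HbA1c <7.0%.

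Four other places bear on the point:
- Section 6.1: "Number of subjects expected to complete the trial: 340", out of 426 randomised.
- Section 17.3: "The main reasons for withdrawal/discontinuation are expected to be ineffective therapy and adverse events".
- Section 8.1.7: when a subject withdraws, "the investigator must aim to undertake procedures similar to those for Visit 26 as soon as possible".
- Section 17.3 also specifies, for a sensitivity analysis of the primary endpoint, 100 imputed data sets whose results "are pooled to one estimate and associated standard deviation using" Rubin's formula.

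**The concern.** A predicted value is an estimated mean. It has no residual scatter, and its estimation error is shared by every subject in the same arm who needs a value. A small shift in the arm's fitted mean moves many imputed subjects across 7.0% together, yet the logistic regression counts each as an independent observation. The reported standard error is then too small. The MMRM's validity under MAR for the continuous endpoint does not carry over once its predictions are dichotomised and analysed as data.

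The plan does not say whether the prediction is conditional on the subject's earlier visits or uses only treatment, strata, region and baseline. That choice decides how much week-24 variance the prediction explains, and so how far the error rate moves.

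The second issue is comparability. The composites share a rule and can be compared with each other, but HbA1c <7.0% follows another. A reader who sets it beside the severe-hypoglycaemia composite (marked key in Section 4.2.2.1) would read the gap as the cost of hypoglycaemia. The triggers differ too: one rule acts on a missing HbA1c, the other on withdrawal, so a subject who stays in but lacks the week-24 sample is covered only by the first. Nor does the plan say whether the sample taken at withdrawal counts as week 24.

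**Working it through.** **1. Inputs from the plan.** Two-sided 5% (Section 17); difference 0.3%, SD 1.1%, 1:1, 213 per arm (Section 17.1); 340 completers (Section 6.1).

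The sample size reproduces. The normal approximation gives 2 × (1.960 + 0.842)² × 1.1² / 0.3² ≈ 211.1, so 212 per arm or 424; the noncentral t gives 426, with power 80.2% at 213 per arm. No power figure is stated for the responder endpoints.

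Expected non-completers: 426 − 340 = 86, and 86/426 = 20.2%. Taking this as the share with no week-24 HbA1c is an assumption.

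**2. What cutting a prediction does.** If the prediction explains a share R² of week-24 variance, the residual SD is 1.1 × √(1 − R²). At R² = 0.5 this is 0.78. A subject predicted at 7.2% then has probability Φ(−0.2/0.78) ≈ 0.40 of being below 7.0%, but is scored as a certain non-responder.

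**3. Type I error, one-predictor simulation.** Both arms have the same mean. Completers are regressed on arm and predictor, missing values are replaced by the fitted mean and cut at 7.0%, and the log odds ratio gets a Wald test. 20,000 runs per cell, 20.2% missing. The slope is the rise in log-odds of withdrawal per SD of predictor towards poorer control.

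| Week-24 mean, withdrawal | R² 0.15 | 0.3 | 0.5 | 0.7 | 0.8 |
|---|---|---|---|---|---|
| 7.0, unrelated | 13.7% | 9.1% | 6.9% | 6.1% | 5.3% |
| 7.0, slope 1 | 11.4% | 8.1% | 6.6% | 5.6% | 5.3% |
| 7.0, slope 2 | 9.3% | 6.8% | 5.7% | 5.1% | 4.8% |
| 7.4, unrelated | 10.8% | 9.2% | 6.8% | 6.3% | 5.8% |
| 7.4, slope 1 | 6.7% | 6.9% | 6.1% | 5.5% | 5.3% |
| 7.4, slope 2 | 5.4% | 5.3% | 5.3% | 5.3% | 5.0% |

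With baseline also in the logistic model (6,000 runs), the mean-7.0, unrelated row is 15.4/10.8/7.9/6.6% for R² 0.15/0.3/0.5/0.7. Without baseline, the same row at 10% missing is 8.4/6.7/5.7/5.1%, and at 5% missing 6.6/5.7/5.0/4.9%.

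**4. Type I error, six-visit simulation.** Unstructured covariance, prediction from the subject's own history, dropout depending on the last HbA1c, the planned logistic model. 3,000 runs per row, about 20% dropout.

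| Dropout, mean fall in HbA1c | Complete data | Predicted value | 95% CI coverage | Model SE / true SE |
|---|---|---|---|---|
| Even, 1.3 | 5.0% | 7.3% | 92.9% | 0.92 |
| Early, 1.3 | 5.1% | 9.0% | 91.0% | 0.88 |
| Early, 1.6 | 5.0% | 9.6% | 90.4% | 0.84 |
| Even, 1.0 | 5.1% | 6.9% | 93.1% | 0.93 |

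At 10% dropout the predicted value gives 6.4–6.8%, at 5% dropout 5.5%. A further six-visit simulation with about 16–23% missing gave 7–10% when conditioning on history and 10–20% with fixed effects only.

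**5. Bias under a true 0.3% difference.** With arm means 6.85 and 7.15 the true response difference is Φ(0.15/1.1) − Φ(−0.15/1.1) = 10.8 points; the predicted value gives 10.9–14.2. At 7.25/7.55 it moves from 10.2 to 9.8–11.6, and at 7.65/7.95 from 8.3 to 7.3–8.5. In the six-visit runs the log odds ratio was 0.54–0.56 against 0.49 with complete data.

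**6. Gap created by the two rules.** With mean 7.0 and unrelated withdrawal, half of the missing subjects are predicted below 7.0%, so the gap is 0.5 × 20.2 = 10.1 points. With mean 7.4 it is 3.6–6.9 points. If poor responders withdraw more, it is 1.7–4.7 points (mean 7.0) or 0.2–2.4 (mean 7.4). The six-visit runs give about 4 points (36–37% against about 33%). Severe hypoglycaemia in an assumed 0.5–2% of responders would add under 1 point.

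**7. Multiple imputation in the same settings.** One-predictor model, 100 sets, 4,000 runs: 3.4–4.0%, against 6.2–14.1% for the single value. Six visits, 20 draws, 400–900 runs: 3–4%, coverage 96–97%.

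**The case against.** The strongest reply is that the high error rates need a weak prediction. The MMRM in Section 17.3 covers weeks 4 to 24 with unstructured covariance, and using a subject's earlier visits is its natural use. Unrelated withdrawal also sits badly with the plan's own expectation that ineffective therapy will be a main reason for leaving. This stands in part: about 7–10% is the figure to lead with, and 15% or more belongs to the baseline-only reading. But the text leaves that reading open, and the 7–10% already comes from dropout that depends on the last HbA1c.

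The share missing may be below 20.2%, since withdrawing subjects are asked for an end-of-treatment sample and Section 18.4 retains such data. That stands; at 5–10% missing the inflation is small.

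Different rules are not in themselves a defect. An HbA1c model cannot predict hypoglycaemia over 24 weeks, so non-response is an understandable rule for the composites. Nor is it a safe benchmark for the treatment contrast: with dropout odds doubled in one arm it rejected a true null in 18.5% of runs, against 10.6% for the predicted value. Both points stand. They rule out simply switching HbA1c <7.0% to that rule, but they do not make the rates comparable.

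Finally, the existing imputation procedure draws both arms from BID parameters, so a MAR version needs its own imputation model. Whether the withdrawal sample counts as week 24 also reaches beyond this endpoint. Both are fair; Section 17 allows a separate SAP before database lock, where they can be settled.

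**Conclusion.** The concern holds. As written, the interval and p-value for HbA1c <7.0% tend to be anti-conservative: about 7–10% true error at a nominal 5% with roughly 20% missing and history-based prediction, with a model standard error 7–16% too small. The error is near nominal if prediction is strong or few values are missing, and 10–20% in the six-visit runs if only fixed effects are used. The treatment effect can be overstated, but that bias vanishes or reverses at higher mean HbA1c. The missing-data rules alone can separate HbA1c <7.0% from the severe-hypoglycaemia composite by 0.2 to 10 points; no such claim is made for the BG-confirmed composite.

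These figures rest on assumptions that the documents do not supply: the share of missing HbA1c, the strength of prediction, the week-24 means, and the timing and cause of withdrawal. The endpoint is supportive and not marked key, and the primary conclusion does not depend on it. This is a change worth considering, held with medium confidence.

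**What to change.** For HbA1c <7.0%, replace the single predicted value by multiple imputation under MAR: 100 data sets, imputed by arm from baseline HbA1c, strata, region and all earlier visits. Derive responder status in each set, fit the planned logistic model and pool by Rubin's rule. Add one table of HbA1c <7.0% with withdrawn subjects as non-responders, so that all three endpoints can be read under one rule; it should not replace the main analysis. State whether an HbA1c sample taken at early withdrawal counts as week 24. The composites can keep their rule.

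The cost is SAP wording, some programming (100-fold imputation and pooling are already planned, though the imputation model differs) and one extra table. The reported interval widens somewhat: in the six-visit runs the mean model standard error rose from 0.213 to 0.227 (0.227/0.213 = 1.07). The test becomes slightly conservative, at 3–4%.

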17.4.1.2 Safety endpoints

All safety endpoints will be summarised and analysed using the safety analysis set. Unless otherwise specified safety endpoints will be analysed by descriptive statistics only.

Adverse events

All AEs will be coded using the most recent version of the MedDRA coding. A TEAE is defined as an event that has onset date (or increase in severity) on or after the first day of exposure to trial product and no later than 7 days after the last day on trial product.

TEAEs are summarised descriptively and displayed in terms of the number of subjects with at least one event (N), the percentage of subjects with at least one event (%), the number of events (E) and the event rate per 1000 years of exposure (R)

Summaries of TEAEs and of serious TEAEs will be presented as an overview including all AEs, serious AEs, number of deaths, AEs by severity, AEs by relation to treatment and AEs leading to withdrawal.

Furthermore summary tables based on system organ class and preferred terms are made for:

- All TEAEs
- Serious TEAEs
- Possibly or probably related TEAEs
- Severe, moderate and mild TEAEs
- TEAEs with preferred term that are experienced by at least 5% of the subjects in any treatment arm or by at least 5% of all subjects
- TEAEs leading to withdrawal

Definition of Hypoglycaemia

Treatment emergent: hypoglycaemic episodes will be defined as treatment emergent if the onset of the episode occurs on or after the first day of trial product administration, and no later than 7 days after the last day on trial product.

Nocturnal hypoglycaemic episodes: are episodes with time of onset between 00:01 and 05.59 both inclusive.

[figure not shown]
Hypoglycaemic episodes are classified according to the Novo Nordisk classification of hypoglycaemia (see [Figure 17–1](#)) and the ADA classification of hypoglycaemia (see [Figure 17–2](#)).

Novo Nordisk classification of hypoglycaemia

In normal physiology, symptoms of hypoglycaemia occur below a plasma glucose level of 3.1 mmol/L (56 mg/dL)²¹. Therefore, Novo Nordisk has included hypoglycaemia with plasma glucose levels below this cut-off point in the definition of blood glucose (BG) confirmed hypoglycaemia.

Novo Nordisk uses the following classification in addition to the ADA classification:

- Severe hypoglycaemia according to the ADA classification²².
- BG confirmed hypoglycaemia: An episode that is BG confirmed by a plasma glucose value <3.1 mmol/L (56 mg/dL) with or without symptoms consistent with hypoglycaemia.
- Severe or BG confirmed hypoglycaemia: An episode that is severe according to the ADA classification²² or BG confirmed by a plasma glucose value <3.1 mmol/L (56 mg/dL) **with** or **without** symptoms consistent with hypoglycaemia.

[figure not shown]

Note: Glucose measurements are performed with capillary blood calibrated to plasma equivalent glucose values

Figure 17–1 Novo Nordisk classification of hypoglycaemia

ADA classification²² of hypoglycaemia

1. Severe hypoglycaemia: An episode requiring assistance of another person to actively administer carbohydrate, glucagon, or take other corrective actions. Plasma glucose concentrations may not be available during an event, but neurological recovery following the return of plasma glucose to normal is considered sufficient evidence that the event was induced by a low plasma glucose concentration.
2. Asymptomatic hypoglycaemia: An episode not accompanied by typical symptoms of hypoglycaemia, but with a measured plasma glucose concentration ≤ 3.9 mmol/L (70 mg/dL).
3. Documented symptomatic hypoglycaemia: An episode during which typical symptoms of hypoglycaemia are accompanied by a measured plasma glucose concentration ≤ 3.9 mmol/L (70 mg/dL).
4. Pseudo-hypoglycaemia: An episode during which the person with diabetes reports any of the typical symptoms of hypoglycaemia with a measured plasma glucose concentration > 3.9 mmol/L (70 mg/dL) but approaching that level.
5. Probable symptomatic hypoglycaemia: An episode during which symptoms of hypoglycaemia are not accompanied by a plasma glucose determination but that was presumably caused by a plasma glucose concentration ≤ 3.9 mmol/L (70 mg/dL).

Note: Glucose measurements are performed with capillary blood calibrated to plasma equivalent glucose values

Figure 17–2 ADA classification of hypoglycaemia

Data on treatment emergent hypoglycaemic episodes are presented in terms of the number of subjects with at least one event (N), the percentage of subjects with at least one event (%), the number of events (E) and the event rate per 100 years of exposure (R). Separate summaries are made for all hypoglycaemic episodes, nocturnal hypoglycaemic episodes, severe or BG confirmed hypoglycaemic episodes, nocturnal severe or BG confirmed hypoglycaemic episodes and the ADA classification of hypoglycaemia.

The number of treatment emergent severe or BG confirmed hypoglycaemic episodes will be analysed by a negative binomial regression model with a log-link function and the logarithm of the time period in which the hypoglycaemic episodes are considered treatment emergent as offset. The model will include treatment, combination of the two stratification factors and region as factors. The results will include the 95% confidence interval for the event rate ratio (BIAsp TID over BIAsp BID) and p-value as part of the presentation. To the extent where data allow, analyses will be performed on all severe or BG confirmed episodes and nocturnal severe or BG confirmed episodes separately.

Vital signs

Vital signs (systolic blood pressure, diastolic blood pressure and pulse) will be summarised and tabulated by treatment and visit together with the change from the baseline to end-of-treatment.

Laboratory assessments

All continuous laboratory parameters will be evaluated by descriptive statistics and tabulated by visit together with change from baseline to end-of-treatment. Shift tables showing changes from baseline to end-of-treatment (normal and abnormal) will be constructed for each laboratory safety variable. No formal statistical analyses of laboratory parameters will be performed and abnormal values will be listed.

Eye examination and physical examination

For eye examination and physical examination, a shift table for change from baseline to end-of-treatment will be generated. Subjects with any change in examination result will be listed.

Change in body weight after 24 weeks of treatment

Change from baseline in body weight after 24 weeks of treatment will be analysed with a similar method as the primary endpoint, where baseline body weight will replace baseline HbA_{1c} in the model.

Total daily insulin dose

The actual daily insulin dose is recorded on the three random days when 3-point SMPG are performed prior to each visit for visits 3-26. The calculated/prescribed insulin dose is recorded for visits 2-25. The actual insulin dose from the last of the three days and calculated/prescribed insulin dose will be summarized descriptively according to regimen as dose in units and units/kg per visit. Total daily dose, which is the sum of doses given before breakfast and before main evening meal for the BID treatment group, and the sum of doses given before breakfast, before lunch and before main evening meal for the TID treatment group, will also be summarized descriptively as dose in units and units/kg per visit.

